## 2 INTRODUCTION

### 2.1 STUDY RATIONALE

The purpose of the study is to evaluate the safety, tolerability, immunogenicity, and pharmacokinetics (PK) of single ascending intravenous (IV) doses of XTMAB-16 in healthy adult subjects. This study is the first time that XTMAB-16 will be administered to humans. The safety, tolerability and PK results obtained from this study will inform future clinical development of XTMAB-16 for the treatment of sarcoidosis.

XTMAB-16 is being developed as a monoclonal antibody (mAb) tumor necrosis factor alpha (TNF $\alpha$ ) blocker to address the treatment gap for patients with advanced pulmonary sarcoidosis with or without extrapulmonary involvement.

### 2.2 BACKGROUND

#### 2.2.1 SARCOIDOSIS

Sarcoidosis is a chronic systemic disease of unknown etiology and uncertain prognosis that most commonly affects young and middle-aged adults. Sarcoidosis is characterized by the presence of noncaseating granulomas in 1 or more organs. While sarcoidosis is a systemic disease, the lungs, lymphatic system, and skin are most commonly affected. Patients frequently present with pulmonary infiltrates, bilateral hilar lymphadenopathy, and ocular and skin lesions.

A widely accepted hypothesis of the pathogenesis of sarcoidosis is that various unidentified antigens, either infectious or environmental, trigger an exaggerated immune response in

genetically predisposed individuals. In the lung, the antigen is presented to naive CD4+ lymphocytes and alveolar macrophages, activating both cell types, and subsequently triggers a complicated cascade of proinflammatory cytokines. The release of cytokines enhances the expression of tumor necrosis factor  $\alpha$  (TNF $\alpha$ ), a protein that plays a significant role in antigen-stimulated, cell-mediated immune responses. High levels of TNF $\alpha$  released from alveolar macrophages have been shown to correlate with disease progression. Notably, spontaneous release of TNF $\alpha$  by alveolar macrophages is greater in patients with active disease than in those with inactive or corticosteroid-treated disease. Similar inflammatory mechanisms are believed to underlie sarcoidosis involvement in other organs, such as the skin.

To prevent granuloma formation and limit tissue injury and fibrosis, targeted immunosuppression of proinflammatory cytokines such as TNF $\alpha$  is a clear goal of therapy, particularly in patients with chronic sarcoidosis.

Please see the Investigator's Brochure (IB) for additional details.

#### 2.2.2 TNF $\alpha$

TNF $\alpha$  is a proinflammatory cytokine widely recognized and implicated in inflammatory disorders including sarcoidosis.

A model for granuloma formation in sarcoidosis patients suggests that macrophages, dendritic cells, and lymphocytes, with the aid of cytokines and chemokines, collaborate with one another. TNF $\alpha$ , one of the participating cytokines in the formation of the sarcoid granuloma, along with the successful use of immunomodulators inhibiting TNF $\alpha$  such as pentoxifylline and thalidomide, led to the increasing utilization of anti-TNF agents in sarcoidosis patients. In patients with severe refractory sarcoidosis who do not respond to conventional immunosuppressive treatment, TNF $\alpha$  inhibitors infliximab and adalimumab are recommended by the World Association of Sarcoidosis and other Granulomatous Disorders (WASOG). Comparisons between TNF $\alpha$  inhibitors have shown that infliximab is superior to other anti-TNF therapies.

Please see the IB for additional details.

### 2.2.3 XTMAB-16

XTMAB-16 is a chimeric human-murine IgG1κ anti-TNFα monoclonal antibody with a molecular weight of ~149 kDa. Extensive analyses have been conducted to demonstrate the physico-chemical properties and pharmacology of XTMAB-16 as a TNFα inhibitor.

[REDACTED]

[REDACTED]

[REDACTED]

[REDACTED]

In a Good Laboratory Practices (GLP) 13-week hTNF transgenic (TgTC) mouse toxicology study, the inhibitory effect of KBMAB-16 (clinical drug product XTMAB-16) as a TNFα blocker and its potential pharmacologic benefit were demonstrated by comparing the arthritis scores in joints of vehicle and test-article treated animals using both clinical observations and histopathological examinations. The study determined that there was statistically significant improvement in arthritis scores in the KBMAB-16 treated groups which received 10, 20, or 40 mg/kg of XTMAB-16 as compared to the vehicle control group, starting at week 5 (Day 36) until the end of the study at week 17 ( $p < 0.01$  or  $p < 0.05$ ).

XTMAB-16 is currently being developed as a novel biologic product for the treatment of patients with advanced pulmonary sarcoidosis with or without extrapulmonary involvement.

#### Clinical Overview

This will be the first clinical study ever performed for XTMAB-16. No previous clinical data are available for this study drug.

[REDACTED]

[REDACTED]

[REDACTED]

[REDACTED]

[REDACTED]

[REDACTED]

Please see the IB for additional details.

### 2.2.4 TOXICOLOGY OVERVIEW

The 6-week GLP, TgTC mouse, toxicology study included: (1) a main (toxicity) study (60 animals, 10 /sex/dose; vehicle vs 20 mg/kg vs 40 mg/kg), with a 4-week treatment period followed by a 2-week recovery period, to evaluate the toxicity of KBMAB-16 (clinical drug product XTMAB-16) from 3 biweekly IV injections (Days 1, 15, 29); and, (2) a satellite (toxicokinetic [TK]) study

(132 animals, 2/sex/dose/time point for 10 time points) to characterize a single IV dose TK profile. The findings are summarized below.

KBMAB-16 was well tolerated up to 40 mg/kg after 3 biweekly IV injections. All animals survived in the toxicity study with no meaningful abnormal clinical and pathological findings. Thus, the no adverse effect level (NOAEL) of KBMAB-16/XTMAB-16 was considered to be 40 mg/kg via 3 biweekly IV injections in TgTC mice.

In the TK groups, a complete 6-week (1008 hours) TK profile following a single dose (10 mg/kg, 20 mg/kg and 40 mg/kg) of KBMAB-16 was obtained. After a single 40 mg/kg IV injection, the maximum observed concentration ( $C_{max}$ ) was at 791.0  $\mu$ g/mL and the area under the concentration-time curve ( $AUC_{0-\infty}$ ) was at 124257.2  $\mu$ g\*hr/mL. The systemic exposure in terms of  $C_{max}$  and  $AUC_{0-\infty}$  were increased proportionally in the dose range from 10 to 40 mg/kg of KBMAB-16. The half-life ( $t_{1/2}$ ) of XTMAB-16 ranged from 9.4 days (226.9 hr) at 10 mg/kg to 13.6 days (327.2 hr) at 40 mg/kg, which is comparable to the half-life of 10 mg/kg of infliximab in humans of 13.9 days (335.1 hr).

In a 13-week, repeated dose, GLP, toxicology study (Study 14042-20005) in hTNF $\alpha$  transgenic mice, KBMAB-16 was well tolerated up to 40 mg/kg after 7 bi-weekly IV injections in TgTC animals in the toxicity study with no meaningful test article related clinical and pathological abnormalities observed. The NOAEL of KBMAB-16 was considered to be 40 mg/kg after 7 doses biweekly IV injection in TgTC mice. In addition, safety pharmacology assessments of the central nervous system (CNS) and respiratory systems did not reveal adverse effects at any dose of KBMAB-16. After 40 mg/kg IV injection for 6 doses, the  $C_{max}$  was 1104.9  $\mu$ g/mL, the  $(AUC)_{0-\infty}$  was 624865.9  $\mu$ g\*hr/mL and the  $(AUC)_{0-\tau}$  was 124878.7  $\mu$ g\*hr/mL. The systemic exposure in terms of  $C_{max}$  and  $(AUC)_{0-\infty}$  increased in a dose proportional manner in the dose range from 10 to 40 mg/kg of KBMAB-16.

For further detailed nonclinical data for XTMAB-16, refer to the IB.

#### Risk/Benefit Assessment

This is the first time that XTMAB-16 will be administered to humans. XTMAB-16 is not expected to provide any clinical benefit to healthy participants. This study is designed primarily to generate safety, tolerability, immunogenicity, and PK data to provide the basis for further clinical development of XTMAB-16 as a potential new, pharmacological agent for the treatment of sarcoidosis. As such, data from this study may benefit people with sarcoidosis in the future.

As of the issuance of this protocol, no specific human risks have been identified based on data gathered during a nonclinical study with XTMAB-16 using a transgenic mouse model (see IB). The clinical impact of any potential risks will be minimized through cautious dose escalation; that is, higher doses of XTMAB-16 will be administered only after lower doses have been found to be well tolerated with an acceptable safety profile. In addition, this study includes standard, intensive, inpatient monitoring of the participants following administration of single, IV doses of the investigational product. Clinical safety laboratory tests, thorough assessments of vital signs,

electrocardiograms (ECGs), physical examinations, and adverse event (AE) monitoring will provide essential data to evaluate the safety and tolerability of XTMAB-16 in humans.

TNF $\alpha$  blockers have been extensively studied and their risks are well characterized. The known risks of TNF $\alpha$  blockers are similar across the drug class. According to the TNF $\alpha$  blocker package inserts, the most significant risks [noted as a black box warning] include.

- Serious infection or sepsis (including tuberculosis, histoplasmosis, coccidioidomycosis, candidiasis, aspergillosis, blastomycosis, pneumocystosis, Legionella, and Listeria)
- Malignancy (including hepatosplenic T cell lymphoma)

To reduce the risk of infection or sepsis in this study, healthy participants without active infections will be enrolled. Additionally, participants with a medical history of conditions known to be at risk for AEs with TNF $\alpha$  blockers (eg, tuberculosis, hepatitis) or who have lived in or traveled to areas of endemic tuberculosis or endemic mycoses are excluded from participation.

While malignancy cannot specifically be prevented or reduced, most of the patients who reported malignancies after taking TNF $\alpha$  blockers were also taking concomitant immunosuppressants. In this study of healthy participants, participants requiring immunosuppressants will be excluded, thus the Sponsor considers the risk of malignancy in this study to be very low.

Additional contraindications noted for TNF $\alpha$  blockers include:

- Patients with moderate to severe heart failure (for doses >5 mg/kg)
- Patients with severe hypersensitivity reactions to infliximab products or components.

To mitigate the risk to patients with moderate to severe heart failure, participants with known cardiac conditions will be excluded from this study and all participants will be closely monitored for 2 hours after infusion (and up to 4 hours at the Investigator's discretion). Participants will be closely monitored for 2 hours after infusion (up to 4 hours at Investigator discretion). Injection site reactions will be graded according to [Table 9](#). Hypersensitivity reactions, including any instances of anaphylaxis, will be monitored and treated as noted in [Appendix 5](#). Given the above precautions for this study, the Sponsor considers the risk of cardiac conditions and hypersensitivity in this study to be low.

Taking into account that (1) XTMAB-16 is a TNF $\alpha$  blocker, a class of drug with a known safety profile, and (2) the measures taken to minimize risk to participants of this study, the potential

risks identified in association with XTMAB-16 are justified by the anticipated benefit, in terms of contribution to the process of developing new therapy in an area of unmet medical need.

### 3 OBJECTIVES AND ENDPOINTS

OBJECTIVES	ENDPOINTS	JUSTIFICATION FOR ENDPOINTS
To evaluate the safety, tolerability, immunogenicity, PK, and selected clinical biomarkers after a single IV infusion of XTMAB-16 at 2 and 4 mg/kg doses in normal healthy participants.	
Safety and Tolerability
 
The incidence of treatment-emergent adverse events (TEAEs) and serious adverse events (SAEs)
 
Observed values and change from Baseline in safety laboratory tests (hematology, clinical chemistry, urinalysis) by visit
 
Observed values and change from Baseline in ECG by visit
 
Time-matched Baseline and 50-hr postdose digital ECG monitoring
 
Observed values and change from Baseline in vital signs
 
Immunogenicity
 
Number and percentage of participants by cohort who test positive for XTMAB-16 ADA at Baseline, Day 29, Day 57, and Day 71
 
Number and percentage of participants by cohort who test positive for XTMAB-16 nAb at Baseline, Day 29, Day 57, and Day 71
 
Pharmacokinetics
 
Maximum observed XTMAB-16 concentration (<math>C_{max}</math>)
 
XTMAB-16 serum concentration at the end of drug infusion (<math>C_T</math>)
 
Time to maximum observed XTMAB-16 concentration (<math>t_{max}</math>)
 
Area under the XTMAB-16 concentration-time curve from time zero (predose) extrapolated to infinity (<math>AUC_{0-\infty}</math>)
	The endpoints chosen for this study are standard and commonly accepted for Phase 1 FIH trials to establish initial safety, PK, and immunogenicity in the support of continued investigation of the study drug for clinical development.

OBJECTIVES	ENDPOINTS	JUSTIFICATION FOR ENDPOINTS
	
Area under the XTMAB-16 concentration-time-curve from time zero to (predose) to the last quantifiable time point at <math>t</math> (<math>AUC_{0-t}</math>)
 
Systemic clearance after IV dosing (CL)
 
Apparent terminal half-life (<math>t_{1/2}</math>)
 
Volume of distribution following IV dosing (<math>V_z</math>)
 
Mean residence time (MRT)
 
Biomarkers
 
Absolute and percent change from Baseline in the following biomarkers
 

• Angiotensin converting enzyme (ACE)

• soluble IL-2 receptor (sIL-2R)

• Interleukin 6 (IL-6)

• soluble TNF<math>\alpha</math> (sTNF<math>\alpha</math>)

	

Abbreviations: ACE = angiotensin converting enzyme; ADA = anti-drug antibody; IL-6 = interleukin 6; IV = intravenous; PK = pharmacokinetics

## 4 STUDY DESIGN

### 4.1 OVERALL DESIGN

This is a single-center, randomized, double-blind, placebo-controlled, first-in-human (FIH), single IV infusion of sequential ascending doses of XTMAB-16 in normal healthy male and female participants.

A total of 24 normal healthy adult participants will be enrolled and assigned into 2 treatment cohorts with 12 participants (9 on XTMAB-16 and 3 on placebo) in each cohort as shown in [Table 2](#). Participants will receive a single intravenous (IV) infusion of 2 or 4 mg/kg of XTMAB-16 or placebo on Day 1.

**Table 2 Dose Cohorts**

Cohort	Dose	Escalation Factor	XTMAB-16	Placebo a	Total
1	2 mg/kg	-	9	3	12
2	4 mg/kg	2 x	9	3	12

a The matching placebo will be identical to the XTMAB-16 in terms of volume and infusion duration.

For all cohorts, a sentinel group of 2 participants (1 assigned to XTMAB-16 and 1 assigned to placebo) will be dosed at least 48 hours before the remaining participants in the same cohort. To maintain the treatment blind, study treatment will be prepared by an unblinded pharmacist according to the treatment assignment who will appropriately label the study drug for administration in a way that maintains the treatment blind to clinical research unit (CRU) staff and the participant.

After blinded review of the available safety and laboratory data of the sentinel group by the Principal Investigator (PI), if no notable safety signals are identified, the remaining participants within the same cohort will be dosed. Participants within a cohort should be dosed at least 1 hour apart. If there are no safety concerns, the participants in cohort 2 will receive XTMAB-16 after at least 14 to 21 days clinical assessment of the participants at cohort 1. See [Section 4.1.1](#) for additional information on dose escalation.

After a screening period of up to 28 days, participants will be admitted to the CRU on Day -2 for COVID-19 testing and baseline procedures. After confirmation of eligibility, participants will be randomly assigned to treatment (1:1 XTMAB-16 to placebo for sentinel cohort, 3:1 for remaining participants) and administered study drug on Day 1. Participants will remain at the CRU through Day 8 for PK, biomarkers, ADA, and safety assessments, and will be discharged on Day 8 once all procedures for that day have been completed. Participants will return to the CRU on Days 15, 29, 43, 57, and 71 (End of Study/safety follow-up).

Safety assessments will include AEs, safety laboratory assessments, vital signs, ECG, immunogenicity, and physical examination. PK collection and analysis will also be completed in a similar manner during the course of this study.

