**Amendment 3: Summary of Changes from Previous Version (version 3.0 dated 14 May 2021):**

Affected Section(s)	Summary of Revisions Made	Rationale
Cover Page, Investigator's Agreement, 1.1 Synopsis	Study title updated to remove "two-part".	Updated in response to FDA request dated 28 May 2021.
1.1 Synopsis, 1.2 Schema, 1.3 Schedule of Activities, 3 Objectives and Endpoints, 4.1 Overall Design, 4.1 Dose Escalation, 4.3 Justification for Dose, 5.5 Replacement of Participants, 9.2 Sample Size Determination, 9.4.6 Planned Safety Review	Study design updated and "two-part" and relevant description on Part A and Part B removed. The number of cohorts updated from 4 to 2 (now Cohorts 1 and 2), and the total number of participants updated to 24 (12 participants each cohort). Dose of each cohort updated to 2 mg/kg for Cohort 1, and 4 mg/kg for Cohort 2. Study objective updated to reflect the dose. The randomization ratio of participants except for sentinel cohort updated to 4:1. Justification for dose updated accordingly to reflect the revised dose.	Updated in response to FDA request dated 28 May 2021.
6.1.2 Dosing and Administration	Reference to the Pharmacy Manual added, and the dose of each cohort updated.	To refer to the Pharmacy Manual for details. Updated in response to FDA request dated 28 May 2021.

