## 1 PROTOCOL SUMMARY

### 1.1 SYNOPSIS

**Title:** A Randomized, Double-blind, Placebo-controlled First-in-Human Study to Evaluate the Safety, Tolerability, and Pharmacokinetics of a Single Intravenous Infusion of XTMAB-16 in Healthy Adult Participants

**Study Description:** This is a single-center, randomized, double-blind, placebo-controlled, first-in-human, single intravenous (IV) infusion of sequential ascending doses of XTMAB-16 (formerly referred to as KBMAB-16) in normal healthy male and female participants.

A total of 24 normal healthy adult participants will be enrolled and assigned into 2 treatment cohorts with 12 participants (9 on XTMAB-16 and 3 on placebo) in each cohort.

Cohort	Dose a	Escalation Factor	XTMAB-16	Placebo a	Total
1	2 mg/kg	-	9	3	12
2	4 mg/kg	2 x	9	3	12

a The matching placebo will be identical to the XTMAB-16 in terms of volume and infusion duration.

For all cohorts, a sentinel group of 2 participants (1 assigned to XTMAB-16 and 1 assigned to placebo) will be dosed at least 48 hours before the remaining participants in the same cohort. After blinded review of the available safety and laboratory data of the sentinel group by the Principal Investigator (PI), if no notable safety signals are identified, the remaining participants within the same cohort will be dosed. Participants within a cohort should be dosed at least 1 hour apart.

If there are no safety concerns after completion of Cohort 1, the participants at cohort 2 will receive XTMAB-16 after 14 to 21 days clinical assessment of the participants at cohort "n-1."

After a screening period of up to 28 days, participants will be admitted to the clinical research unit (CRU) on Day -2 for COVID-19 testing and baseline procedures. After confirmation of eligibility, participants will be randomly assigned to treatment (1:1 XTMAB-16 to placebo for sentinel cohort, 4:1 for remaining participants) and administered study drug on Day 1. Participants will remain at the CRU through Day 8 for pharmacokinetics (PK), biomarkers, anti-drug antibodies (ADA), and safety assessments, and will be discharged on Day 8 once all procedures for that day have been

completed. Participants will return to the CRU on Days 15, 29, 43, 57, and 71 (End of Study/safety follow-up).

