### 9.2 SAMPLE SIZE DETERMINATION

The selection of 24 participants (12 per cohort) was based on feasibility and precision around the estimates for target variables associated with the primary and secondary endpoints. No sample size calculation was performed.

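### Protocol Section 4.1 gives a 3:1 ratio for the non-sentinel participants, where Table 2 requires 4:1 and the synopsis and SAP state 4:1

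*Protocol*

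**What the plan says.** Protocol Section 4.1 plans "12 participants (9 on XTMAB-16 and 3 on placebo) in each cohort", and Table 2 in that section repeats these counts for both dose levels. The section also sets a sentinel pair in each cohort, one participant on each treatment. Its paragraph on admission and randomisation then gives the allocation as "1:1 XTMAB-16 to placebo for sentinel cohort, 3:1 for remaining participants".

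The synopsis (Section 1.1) has the same cohort counts and the same sentinel pair, but gives the allocation as "1:1 XTMAB-16 to placebo for sentinel cohort, 4:1 for remaining participants". SAP Section 3.1 also has 4:1, with the same counts.

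Protocol Section 6.3, on randomisation and blinding, states no ratio, block size or list structure. SAP Section 3.1.1 does not either. Section 9.2 says of the total of 24: "No sample size calculation was performed".

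**The concern.** Two different ratios are in force for the same participants, and the one in Section 4.1 does not fit the table in its own section. Apart from the synopsis and the amendment log, Section 4.1 is the only place in the protocol that states this ratio. A reader who works from the main text therefore meets only the figure that does not fit.

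The ratio is an input to the randomisation schedule. Under Section 6.3 a third-party unblinded statistician generates that schedule and it goes to the pharmacist before the study starts, so blinded staff would not readily notice a wrong split. If 3:1 were applied to the non-sentinel participants, a cohort could end with fewer than nine people on XTMAB-16. In a first-in-human study those participants supply the PK data and the safety data on drug.

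The SAP does not record the conflict. It names protocol version 4.0, Amendment 3 as its basis (Section 1), uses 4:1, and reports no changes to the planned analysis (Section 4.14).

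**Working it through.** **Inputs from the documents**
- Cohort size 12, with 9 on XTMAB-16 and 3 on placebo (Protocol Section 4.1 and Table 2; synopsis; SAP Section 3.1).
- Sentinel pair of 1 + 1 (same places).
- Ratio k:1 among the rest: k = 3 in Protocol Section 4.1; k = 4 in the synopsis and SAP Section 3.1.

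**Formula.** The remaining participants number 12 − 2 = 10. Active per cohort = 1 + 10k/(k+1). Placebo per cohort = 1 + 10/(k+1).

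**Reproducing the planned split.** With k = 4: active = 1 + 8 = 9 and placebo = 1 + 2 = 3. This matches Table 2 exactly and gives 18:6 over two cohorts. Working backwards, (9 − 1):(3 − 1) = 8:2 = 4:1.

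**With the Section 4.1 ratio.** With k = 3: active = 1 + 7.5 = 8.5 and placebo = 1 + 2.5 = 3.5, or 17:7 over two cohorts. The 10 cannot be divided this way. Rounding gives 7:3 (cohort 8:4) or 8:2 (cohort 9:3, but then the ratio actually used is 4:1). The ratio 3:1 does describe the whole cohort, since 9:3 = 3:1.

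**How often 9:3 would be missed if 3:1 were used.** The documents give no scheme, so each line below is an assumption.

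| Assumed scheme at 3:1 | Chance that a given cohort gets 8:2 | Chance that at least one of two cohorts misses 9:3 |
|---|---|---|
| Separate list per cohort, permuted blocks of 4 | 1/2 | 1 − (1/2)² = 0.75 |
| Simple randomisation | 45 × 0.75⁸ × 0.25² = 0.28 | 1 − 0.28² = 0.92 |
| One continuous list, permuted blocks of 4 | 1/2 | 1 |

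- Separate lists: two full blocks give 6:2. The last two places come from a third block of 4, and they avoid its one placebo slot with probability C(3,2)/C(4,2) = 3/6 = 1/2.
- Continuous list over all 20 non-sentinel participants: the third block straddles the two cohorts. Its single placebo slot falls in exactly one of them, so one cohort always ends 8:4 and the other 9:3.
- Under either block scheme, an affected cohort ends 8:4.
- The 0.92 is mostly due to simple randomisation itself. At 4:1 the chance of exactly 8:2 is 45 × 0.8⁸ × 0.2² = 0.30, and at least one cohort misses with probability 1 − 0.30² = 0.91.

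**The case against.** The best defence is that the documents settle the question themselves. Section 4.1 states 9 and 3 per cohort and a 1 + 1 sentinel pair, which leaves 8:2 as the only possible split. The synopsis and SAP agree. The Amendment 3 summary says "The randomization ratio of participants except for sentinel cohort updated to 4:1" and lists Section 4.1 among the sections affected. To build the schedule at 3:1, its author would have to ignore all of this. The consequence would also be small: no hypothesis is tested (Section 9.1), no sample size was calculated, placebo is pooled across cohorts for safety (SAP Section 4.2), and an 8:4 cohort differs from plan by one participant. These points stand and they limit the severity. They do not make the Section 4.1 sentence right.

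Three stronger readings are tempting, and the documents do not support them:
- **That 3:1 makes 9:3 impossible.** It is impossible only as an exact ratio on 10 people. A cohort could still reach 9:3 by chance, with probability 0.28 to 0.50 under the schemes above.
- **That 3:1 is the old ratio left in place.** The amendment summary never says what the ratio was before. The figure could equally be the whole-cohort ratio put in the wrong sentence. The finding rests on the current text alone.
- **That the schedule was built wrongly.** Neither document shows the schedule or says which ratio it used.

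**Conclusion.** The ratio in Protocol Section 4.1 is wrong as written. It conflicts with Table 2 in the same section, with the synopsis and with SAP Section 3.1. Only 8:2 among the 10 non-sentinel participants reconciles all the stated counts. That conclusion is arithmetic on the documents' own figures and needs no assumption.

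The possible damage does depend on assumptions. If a schedule had been built at 3:1, at least one cohort would miss 9:3 with probability of about 0.75 to 1 across the three schemes tried. Under a block scheme, an affected cohort would have 8 rather than 9 on XTMAB-16, a loss of 1/9, or 11%.

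The severity is moderate. The allocation ratio is an operative design figure, so this is more than a slip of style. But the intended split is unambiguous, and no power figure, test or analysis set changes.

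**What to change.** In the randomisation sentence of Protocol Section 4.1, replace 3:1 with 4:1 so that it agrees with the synopsis and SAP Section 3.1. The SAP needs no change on this point.

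Also have the unblinded statistician confirm that the schedule for each cohort is 1:1 for the 2 sentinels plus exactly 8:2 for the other 10. The check should be made on counts, because under simple randomisation even a 4:1 ratio would not guarantee 8:2.

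The cost is a change to one figure in the protocol and one check of an existing schedule. No participants are added and no analysis changes.
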